5.3 Exclusion criteria

This study provides premature withdrawal of the patients from the protocol due to different reasons, that include but not limited to the following:

1. Investigator took decision to withdraw patient according to patient's interests.
2. Sponsor's decision to exclude patient from the study due to serious protocol deviation/protocol violation.
3. Adverse event, requiring cessation of the study therapy, or prescription of prohibited products, declared in the Section "Acceptable and prohibited recent and concomitant therapy", or restricting performance of protocol procedures.
4. Significant concomitant disease that is, according to Investigator's opinion, poses risk to patient's well-being.
5. Patient non-compliance with the study requirements.
6. Pregnancy.
7. Patient decision of not participating in the study (informed consent withdrawal).

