Randomization number, as well as product assigned to the patient, should not be changed during the study. If patients prematurely withdraws from the study, **his/her randomization number never used again**, and patients does not have an ability to return to the study. For patients, prematurely withdrawn from the study, Investigator should fill out correspondent CRF section – Study termination.

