4.3.2 Treatment blinding

This study is performed as open-label so that investigators and participating patients will be aware of the product administered to the patients.

4.4 Description of treatment method applied within the study, dosage and administration schedule of the study product. Description of pharmaceutical form, package and labeling of the study product

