4.5.3.6 Unplanned visit

If patient prematurely withdraws from the study at any stage, it is required, if possible, to perform all procedures associated to premature withdrawal from the study visit within one week following decision of patient withdrawal. Procedures of this visit are identical to the procedures of the end of treatment visit (Visit 6).

Table 5 Timetable of basic procedures of the study

	Visit 1	Visit 2	Visit 3 (2 weeks ± 3 days)	Visit 4 (4 weeks ± 3 days)	Visit 5 (8 weeks ± 3 days)	Visit 6 (12 weeks ± 3 days)	Visit 7 (30 + 5 days after end of treatment)
Days (D)	D from - 14	D1	D15 (±3)	D29 (±3)	D57 (±3)	D85 (±3)	D114 -
Reception of the informed consent	X						
Demographic data ¹ /patient history acquirement	X						
Previous and concomitant therapy assessment	X	X	X	X	X	X	X
Assessment and registration of AE	X	X	X	X	X	X	X
Physical examination ²	X	X	X	X	X	X	X ³
Complete blood count ⁴	X				X	X	
Blood chemistry ⁵	X				X	X	
Urinalysis ⁶	X				X	X	
Serological examination (HIV, Hep B and C)	X						
PSA level assessment (male only)	X						
Pregnancy test (only women with child-bearing potential)	X	X				X	

US-examination of kidneys, bladder and urine excretory ways (residual urine volume assessment)	X						
US examination of the bladder with residual urine volume assessment		X		X	X	X	
Cough probe	X						
12-lead ECG	X					X	
Assessment with OAB Awareness Tool Questionnaire	X	X	X	X	X	X	
Quality of Life assessment with EQ5D Questionnaire		X				X	
Issue/return and assessment of the diary	X	X	X	X	X	X	
Randomization		X					
Study product issue:		X	X	X	X		
Study product return, compliance assessment			X	X	X	X	

¹ Sex, date of birth, race, body mass, height

²Physical examination includes vital parameters assessment

³Is not conducted in case of telephone contact with the patient

⁴Hemoglobin, hematocrit, white blood cells and differential blood count, platelets.

⁵ ALT, AST, bilirubin, creatinine, total protein, glucose, alkaline phosphatase, cholesterol, potassium, sodium

⁶ Specific gravity, pH, protein, urinary sediment

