4.8 Storage of randomization codes

Randomization process description is provided in Section 4.3.1.

List of randomization numbers, generated before the start of the study, will be stored in the study file in center, as well as by Sponsor or his/her Representative. Investigator bears responsibility for randomization performance (assignment of randomization number to the patient) according to this list. Randomization number, assigned to the patient, is recorded in the Screening/patients inclusion log.

Randomization numbers list will be known to investigators, Sponsor, regulatory authorities (in case of serious adverse event recognition).

4.9 List of data registered directly in CRF.

Primary data (source data) contains all information, recorded in original medical documents and approved copies, describing results of clinical observations, investigations and other activity, allowing to reconstruct clinical study course and perform its assessment. Source data are contained in primary documents (original documents or certified copies).

For each patient, participating in this study, electronic case report form (eCRF) is created, containing basic information, associated with the study.

The Sponsor will provide a separate manual (guidance) concerning eCRF handling.

This study does not provide any data that would be included into eCRF without reflection of this information in primary documents. All data, associated with this study, will be originally recorded in primary documents and then in the eCRF.

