5.4 Follow up observation of the patients withdrawn from the study

If patient withdraws from center prematurely it is required to ask him to visit center and, if possible, to complete all visit procedures of the end of the study (Visit 6, Week 12).

Investigator should designate the reason for preterm withdrawal in primary documents and CRF. Whether patient is willing to withdraw from the study of one's own free will, Investigator should try to reveal the reason for his/her decision. If preterm withdrawal is associated with adverse event, Investigator should apply all possible efforts for collection of information concerning his/her outcome and record this information in CRF in adverse events section. If withdrawal from the study is secondary to serious adverse event (SAE), immediate notification of Sponsor about SAE procedure should be followed.

Patients, prematurely withdrawn from the study after the start of receiving of the study therapy, will not be substituted by new patients, and their data will be taken into consideration during final assessment.

When patient withdraws from the study due to SAE, patients is observed during the whole period up to resolution of SAE.

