9.5 Accounting procedures for missing, non-assessable and equivocal data

Missing, non-assessable and equivocal data will not be substituted and considered to the frames of statistical analysis of the results. All missing or equivocal data as well as data, not included into statistical analysis, will be registered according to CRO procedures. All data unaccounted during analysis will be described and justified in final study report.

Before taking decision concerning inclusion of data, obtained during clinical study, into assessment, patients compliance will be evaluated.

Following indicators will be applied:

Taking Compliance (CC) reflects relationship between number of the product doses taken within defined period and doses, prescribed by attending physician.

Formula: TC = number of doses taken: number of prescribed doses x 100%.

Timing Compliance (TiC).

Formula: TC = number of doses taken in the right time: number of prescribed doses x 100%.

Data would not be taken into consideration when “Product receiving compliance” indicator is less than 90%, and “Accuracy compliance” is less than 90%.

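### Removal for a serious deviation or non-compliance ends scheduled efficacy follow-up in an open-label trial, can leave no true Week 12 outcome, and the per-protocol set cannot reveal the selection

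*Combined protocol and SAP*

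**What the plan says.** **Removal.** Section 5.3, repeated in the synopsis, lists reasons for leaving the study early and says the list is not exhaustive. Criterion 2 is the sponsor's "decision to exclude patient from the study due to serious protocol deviation/protocol violation". Criterion 5 is "Patient non-compliance with the study requirements". Neither "serious" nor the degree of non-compliance is defined there, and no blinded or independent review of these decisions is described.

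**Knowledge of allocation.** Section 4.3.2 says that "investigators and participating patients will be aware of the product administered to the patients". Section 4.8 says: "Randomization numbers list will be known to investigators, Sponsor, regulatory authorities (in case of serious adverse event recognition)". Under 4.3.1 the sponsor or its CRO generates the list.

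**After removal.** Section 4.3.1 states that "patients does not have an ability to return to the study". Sections 4.5.3.6 and 5.4 ask, if possible, for one visit with the Visit 6 procedures, "within one week following decision of patient withdrawal". Section 5.4 adds that for patients withdrawn after starting therapy "their data will be taken into consideration during final assessment".

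**Analysis.**
- Section 7.2 defines the diary endpoint as a mean over the interval between two visits.
- Section 9.8 specifies an ANCOVA with baseline as covariate and treatment group as factor.
- Section 9.5 says "Missing, non-assessable and equivocal data will not be substituted" and also sets aside data when the compliance indicators fall below 90%.
- Section 9.7 admits to the FAS anyone with one dose and one efficacy assessment after Visit 2. PP requires all visits up to Visit 6.

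**The concern.** Randomisation protects the comparison only if outcomes are sought from everyone randomised. Here a party that knows the arm can take a patient out after treatment has started, on a criterion not fixed in advance. The plan then stops seeking the outcome that the primary analysis needs. An outcome that was never collected cannot be restored by a later choice of missing-data method, and decisions made with the arm known give little ground for assuming that the loss is unrelated to outcome.

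If removals differ between arms in number or in prognosis, the Week 12 comparison is between selected groups. In a non-inferiority trial, losing the worse-responding patients from the test arm makes the test product look closer to, or better than, the comparator. The usual check is to compare FAS with PP. It does not help here, because the same patients can be missing from both.

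**Working it through.** **1. The plan's own sample size.** Inputs from 9.2: margin 0.8 episodes/day, SD 2.12, one-sided alpha 0.025, power 80%, 1:1 allocation. A true difference of 0 is not stated but is the value that reproduces the result.

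n per arm = 2 × 2.12² × (0.84 + 1.96)² / 0.8² = 110.1, rounded up to 111, or 222 in total. This agrees with the plan. Randomising 300 allows for a loss of (300 − 222)/300 = 26% from all causes. Power is 80.3% at 111 per arm and 90.5% at 150. The allowance protects power against random loss, so the question here is bias and not sample size.

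**2. What happens to a removed patient.**

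| Time of removal | Week 8–12 diary | FAS membership | Value in the Week 12 ANCOVA | PP |
|---|---|---|---|---|
| Before any efficacy assessment after Visit 2, no closing visit | None | No | None | No |
| Later, but before Visit 5 | None for the planned interval | Yes | None, unless the closing-visit value is taken as Week 12; no rule given | No |
| After Visit 5 | Partial, if the closing visit takes place | Yes | Depends on the same missing rule | No |

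In the second row, taking the closing-visit value as Week 12 would put an earlier value in place of the later one. That sits poorly with the no-substitution rule in 9.5 and is still not a Week 12 outcome.

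**3. Size, as an illustration.** The removal fraction and the outcome gap below are assumptions; neither is in the documents. Let a fraction f of the test arm be removed with no Week 12 value, and let their mean change be D episodes/day worse than that of the rest of the arm. The control arm is untouched.

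- Bias = f × D, towards non-inferiority.
- SE = 2.12 × √(2/n): 0.285 at n = 111 and 0.245 at n = 150. These bracket the number likely to be analysed.
- One-sided error when the true difference equals the margin = Φ(−1.96 + bias/SE).

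| f | D | Bias | Share of margin | Error, 111/arm | Error, 150/arm |
|---|---|---|---|---|---|
| 0 | – | 0 | 0% | 2.5% | 2.5% |
| 5% | 1.0 | 0.05 | 6% | Φ(−1.784) = 3.7% | Φ(−1.756) = 4.0% |
| 10% | 1.5 | 0.15 | 19% | Φ(−1.433) = 7.6% | Φ(−1.347) = 8.9% |

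**4. The opposite selection.** If the removed test-arm patients did better than the rest by the same amounts, the sign reverses. At a bias of −0.15 the error at the margin falls to Φ(−1.96 − 0.527) = 0.6% at 111 per arm. Power at a true difference of 0 falls from 80.3% to Φ(0.65/0.285 − 1.96) = 63%. Equal removal of similar patients from both arms gives no bias in the difference.

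**The case against.** The best defence is that the plan does not discard these patients. It asks for a closing visit with full Visit 6 procedures including the diary, says their data will be used, keeps most of them in the FAS, and continues follow-up of serious adverse events and of adverse events that led to withdrawal. The stated reasons for removal concern conduct, not response. All of that stands, and it rules out several stronger readings that a reader might infer:

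- **That all data collection ends.** Only scheduled efficacy follow-up ends, after the closing visit. A patient removed after Visit 5 may have a partial Week 8–12 diary.
- **That the FAS analysis certainly omits them.** This is an inference from 9.5 and 9.8. What the documents show is a missing rule for the closing-visit value. Only the PP exclusion is certain.
- **That the sponsor decides on non-compliance.** Criterion 5 names no decision-maker.
- **That removal follows running diary results.** Nothing in the documents links exclusion to response.
- **That the bias favours the test product.** The direction depends on who is removed and from which arm.
- **That 26% is the rate of such removals.** It is the all-cause allowance implied by 300 and 222.

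The bracketed condition in 4.8 could be read as limiting the sponsor's knowledge too. It most naturally qualifies the regulatory authorities, and the sponsor or its CRO generates the list in any case.

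There is also a real trade-off. Keeping patients who took little study drug or a prohibited medicine can pull the arms together, which itself favours non-inferiority.

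What survives is that arm-aware removal is permitted on undefined grounds, the planned outcome is then not sought, and the statement in 5.4 that the data will be considered has no analysis rule behind it.

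**Conclusion.** The concern holds as a weakness in design and data collection that should be corrected; it is not evidence that selection will occur. For patients removed before Visit 5 there is no true Week 12 outcome on any reading, and they can be absent from the primary result in both analysis sets.

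The illustrated error of about 4–9% against a nominal 2.5% rests on four assumptions: 5–10% of the test arm removed, outcomes 1.0–1.5/day worse than the rest, no corresponding removal from the control arm, and an SD of 2.12. It also uses the one-sided 0.025 level of 9.2 and the 97.5% interval of 9.3, although 9.8 mentions a one-sided 95% interval. With few removals, or removals balanced between arms, the effect is close to zero; with the opposite selection it works against non-inferiority.

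**What to change.** For criteria 2 and 5, separate leaving the PP set from leaving the study. Record the deviation, exclude the patient from PP only, continue the diary and planned visits to Visit 6 unless consent is withdrawn, and analyse the patient in the FAS as randomised. Section 9.7 already distinguishes deviations that lead out of the study from those that lead out of PP, so the structure exists.

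Wording to amend:
- 5.3, 5.4 and the synopsis, for the two criteria.
- 4.3.1, so that the bar on return does not block continued follow-up.
- 4.5.3.6, so that a single closing visit is not the end of data collection for these patients.
- 9.5, limiting the rule on compliance below 90% to the PP set. Otherwise it would drop many of the same patients from the FAS analysis, and it conflicts with 5.4 as it stands.

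The cost is amendment text and already scheduled visits for a few patients. Where the non-compliance consists of missed diaries or visits, continued follow-up will recover less. Including non-adherent patients may draw the arms together in the FAS; the existing PP analysis is there to check that. Nothing is proposed about whether treatment continues.

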5.4 Follow up observation of the patients withdrawn from the study

If patient withdraws from center prematurely it is required to ask him to visit center and, if possible, to complete all visit procedures of the end of the study (Visit 6, Week 12).

Investigator should designate the reason for preterm withdrawal in primary documents and CRF. Whether patient is willing to withdraw from the study of one's own free will, Investigator should try to reveal the reason for his/her decision. If preterm withdrawal is associated with adverse event, Investigator should apply all possible efforts for collection of information concerning his/her outcome and record this information in CRF in adverse events section. If withdrawal from the study is secondary to serious adverse event (SAE), immediate notification of Sponsor about SAE procedure should be followed.

Patients, prematurely withdrawn from the study after the start of receiving of the study therapy, will not be substituted by new patients, and their data will be taken into consideration during final assessment.

When patient withdraws from the study due to SAE, patients is observed during the whole period up to resolution of SAE.

6 PATIENTS MANAGEMENT

6.1 Description of study products, including name, dosage, frequency and way of administration, treatment duration and follow-up examination

The study will assess following doses and administration schedules of the products (see also Section 4.4):

- Uritos[®] (Imidafenacin, film-coated tablets; 0,1 mg, Kyorin Pharmaceutical Co. Ltd., Japan), oral, 1 tablet BID after meals (after breakfast and after supper).
- Urotol[®] (tolterodine, film-coated tablets; 2 mg, Zentiva k.s., Czech Republic), oral, 1 tablet BID after meals (after breakfast and after supper).

Distribution will be performed according to 1:1 randomization.

Investigator's file will contain batch numbers of the study product and comparator product.

First dose of the product will be issued to the patients at the day of randomization. Administration of this dose will be performed during research center visit. Products will be issued directly to patients, which should hereinafter take the product by their own and record information concerning intake of the study product into diary.

It is recommended to keep 12-hours interval between administrations of the study product. In case of missing dose of the product it should be taken as quickly as possible, however if less than 6 hours left from planned dose, dose is considered to be missed, the next dose should be taken as usual, without doubling dose.

Patients should be instructed and reminded to return all empty packages of study products (including empty and partially used) during each visit to the study physician.

6.2 Medicines allowed and not allowed before and/or during the study.

During the whole study period patient are allowed to receive therapy for primary and concomitant diseases, in case of correspondent indications and absence of significant changes in administration schedule of the existent medicinal therapy within the last month after the study.

During the whole period of administration of the study therapy and following groups of medicines are prohibited for OAB syndrome treatment (except the following):

- M-cholinergic antagonists, including those with selective action, except topic and inhalatory products
- Agents, decreasing urinary bladder activity (toxins)
- All antidepressants
- Alfa-1-adrenergic blocking agents
- Urine formation diminishing agents (vasopressin analogs)
- Prostaglandins synthesis inhibiting agents

Moreover, concomitant prescription of medicinal products from the following groups with possible pharmacokinetic and pharmacodynamic interaction is prohibited.

- Antibiotics from macrolides group (erythromycin, clarithromycin)
- Antifungal agents (ketokonazole, intrakonazole, mikonazole)
- Neuroleptics, barbiturates and other psychotropic agents
- Other medicines strong inductors or inhibitors of cytochromes P450 2D6 and 3A4.
- M-cholinergic agents

Drug-free management of OAB:

Drug-free methods of OAB treatment (e.g. behavioral therapy, Kegel exercises) – are allowed during the study.

Surgical treatment of OAB:

When surgical intervention is required, patient with OAB should be excluded from the study.

No other restrictions concerning daily life, physical activity and diet were not prescribed.

6.3 Measures for control over patients' compliance with study procedures

Compliance assessment will be performed by diary where patient should record data concerning product receipt, as well as be control of amount of product, issued at visits 2, 3, 5 and 5 and returned at visits 3, 4, 5 and 6.

Before participation in the study patients will be informed about risks and restrictions associated with the study. Investigator possesses the right to deny patient's participation in the study in case of his/her suspicion of further study procedures violation from the patient's side.

Compliance will be calculated according to the following formula:

$$K (\%) = N (\text{actual administrations}) / N(\text{scheduled administrations}) \times 100\%.$$

Compliance not lower than 95% will be considered as satisfactory.

Control over compliance will be performed by the diary records.

Patient's diary will be issued to patients not only for assessment of efficiency endpoints, but also for additional control over investigation procedures compliance. Diary, among OAB symptoms (number of urinations, incontinence episodes, micturition urgency) should include information concerning administration of the study product and any adverse events. Patient should take his diary with him/her for each visit. Investigator checks regularity and accuracy of diary filling by the patient. When necessary patients can be instructed repeatedly concerning diary filling rules.

7 EFFICIENCY ASSESSMENT

7.1 Set of efficiency parameters:

Primary efficiency criteria:

Change of mean daily number of urination episodes at the 12 week Visit against the Visit of starting therapy.

Secondary efficiency criteria:

- 1) Change of mean daily number of urinary incontinence episodes at the 12 week Visit against the Visit of starting therapy.
- 2) Change of mean daily number of urinary incontinence episodes during daytime (from 7 am to 11 pm) at the 12 week Visit against the Visit of starting therapy.
- 3) Change of mean daily number of urinary incontinence episodes during nighttime (from 11 pm to 7 am) at the 12 week Visit against the Visit of starting therapy.
- 4) Change of mean daily, mean daytime and mean nighttime number of urinary incontinence episodes at the weeks 2, 4, 8 Visits against the Visit of starting therapy.
- 5) Change of mean number of urinary incontinence episodes per week at the 12 week Visit against the Visit of starting therapy.
- 6) Change of mean daily number of urinary incontinence episodes at the weeks 2, 4, 8 Visits against the Visit of starting therapy.
- 7) Changes in overactive bladder symptoms assessment parameters according to Overactive bladder Awareness Tool Questionnaire at Visits 2, 4, 8 and 12 weeks in comparison to the visit before the beginning of therapy.
- 8) Change of quality of life assessment using EQ-5D questionnaire (at the 12 week Visit against the Visit of starting therapy).

